6. STUDY INTERVENTION

Participants will receive seven individual CBT-I delivered by via video-conferencing over the course of eight weeks. Therapists will be doctoral students in clinical psychology supervised by Drs. [name] and [name]. CBT-I is a manualized multi-component intervention that includes sleep restriction, stimulus control, cognitive restructuring, relaxation training, and sleep hygiene. Sleep restriction is designed to restrict time spent in bed to closely match the time actually spent sleeping. A sleep efficiency percentage (the amount of time spent sleeping divided by the amount of time spent in bed) is calculated, and when the individual is able to achieve 85% sleep efficiency, their sleep time is increased. This process continues until the person can achieve a restful night's sleep with few or no disturbances. Stimulus control is based on the theory that the body eventually becomes conditioned to associate the sleep time and setting with arousal (e.g.

only go to bed when sleepy and refrain from lying awake in bed). This technique is designed to break the perpetuating behaviors and re-associate the bed with sleep. Cognitive restructuring addresses the dysfunctional thoughts and beliefs that serve to maintain and exacerbate insomnia. Individuals are taught to monitor these thoughts and beliefs, challenge their validity, and replace them with adaptive cognitions conducive to the sleep process. Relaxation training targets the physiological and cognitive arousal that accompanies insomnia, and sleep hygiene promotes healthy sleep behaviors and environmental conditions.

Treatment fidelity (including adherence, competence, etc.) is critical to the successful delivery of an intervention in practice. [37] All therapists will receive training in the manualized CBT-I protocol and weekly case supervision meetings including video review throughout the duration of the trial with Drs. [name] and [name]. A checklist of the main teaching points to be covered in each treatment session will be reviewed during supervision and adherence to the CBT-I protocol will be examined by calculating a total score on the teaching checklist. Therapists with adherence ratings below 90% will be provided with additional supervision. [name] will rate twenty percent of the video recorded sessions selected at random for treatment adherence. These data will be used if needed in addition to the Credibility/Expectancy Questionnaire (CEQ)^[38] to examine possible moderators of treatment effects.

7. STUDY PROCEDURES

- **7.1. Initial Screening:** All potential participants will be identified from across Atlantic Canada. Patients will be contacted by the research coordinator and/or primary investigator to explain the study procedures in detail. A brief medical, psychological, and sleep disorders screening questionnaire will be administered to screen for the presence of other medical and/or psychological disorders that may interfere with the participant's ability to participate in the study. This will occur over the telephone.
- **7.2 Informed Consent:** Informed consent will be obtained in two phases. In phase one, participants will be read a simplified consent form over Zoom. In phase two, participants will be given a link to the full consent form and participants will be considered consented when they check the box on the Qualtrics form. This will occur at the time of their initial screening or will be scheduled for a more convenient time prior to the baseline assessment. Once consented, participants will be considered enrolled.
- **7.3. Assessments:** Baseline assessments will be scheduled based on participant availability and will last about 60 minutes. All of the assessments will take place over the secure video conference sessions that will take place in a secure room in the Sleep, Health, and Wellness laboratory. Assessments may also be mailed out to the participants to fill out and return, or participants will be sent a link to the assessments on Qualtrics. During the COVID-19 pandemic, all assessments will follow the usual protocol to take place over the secure video conference platform, however, now this will take place in a secure room in the research coordinator's home. Participants will also be emailed the link to the online component of the assessment which occurs on Qualtrics. No mailing of paper copies of the assessments will occur during the COVID-19 pandemic.

At the baseline assessment, we will assess cognitive function and patient reported outcomes of sleep, fatigue, anxiety, and depression. During the baseline assessment, a member of the study

team will inform the participant if they are randomized to be in the immediate treatment group or the delayed treatment group.

At the mid and post treatment assessments, the participants will also be asked to complete questions related to adverse events during the CBT-I treatment. These questions will be added to their Qualtrics assessment. The open-ended Qualtrics responses will be thematically analyzed to create a record of adverse events experienced by the participants.

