4. STUDY DESIGN

4.1. Overall Design: The proposed trial is an RCT of immediate treatment with CBT-I compared to a waitlist control for PCI in cancer survivors with insomnia (see Figure 2). Participants will receive individual CBT-I delivered by via online video-conferencing over the course of eight weeks. Participants in the waitlist control group will be required to monitor their sleep with sleep diaries for 8 weeks. They will receive CBT-I delivered by via video-conferencing immediately after the waiting period. Both groups will complete follow up assessments three and six months after completing treatment. The total study duration for the immediate and delayed treatment groups is 8 and 10 months, respectively. We chose a waitlist, or delayed treatment, control group because it would be unethical to refuse participants with insomnia the opportunity to receive CBT-I. The use of a waitlist control is also more representative of real-world health care in Canada, where patients will often have to wait for a certain amount of time before receiving treatment and will control for the regression to the mean.

Figure 2: Trial Design

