7.6. Data Collection Schema

The data collection schema for both groups are described in Tables 1a and 1b, followed by details about the instruments. The average time to complete the patient reported outcomes and neuropsychological measures at each assessment time is approximately 45-60 minutes. Participants in both the immediate treatment group and the waitlist treatment group will complete the sleep diaries. Participants will complete the sleep diary upon waking each morning for one week at each assessment period. The time to record the previous night's sleep is approximately 2 minutes. The research team has successfully conducted previous research with similar levels of participant burden. During the COVID-19 pandemic, participants will only complete the diaries if they are able to do so electronically (print and send back electronically, or fill out on their computer and email back). Participants who require a printed copy of the diary to be mailed will not complete the sleep diary component during the pandemic.

Table 1a. Schedule of Assessments and Outcome Collection for Immediate Treatment

Instrument	ТО	T1	T2	Т3	Т4	
	Baseline	Mid- Treatment	Post- Treatment	3 Month Follow Up	6 Month Follow Up	
CEQ	Х					
FACT-COG	X	X	X	X	X	
ISI	X	X	X	X	X	
MFSI-SF	X	X	X	X	X	
HADS	X	X	X	X	X	
WPAI	X		X	X	X	
Sleep Diaries*	X	X	X	X	X	
HLVT-R	X		X	X	X	
COWAT	X		X	X	X	
Digit Span	X		X	X	X	
BRIEF-A	X		X	X	X	
MMSE	X					
Adverse		X	X			
Events						
Protocol						

Table 1b. Schedule of Assessments and Outcome Collection for **Delayed Treatment**

Instrument	T0 Baseline	T1 Monitoring	T2 Pre- Treatment	T3 Mid- Treatment	T4 Post- Treatment	T5 3 Month Follow Up	T6 6 Month Follow Up
CEQ	Χ						
FACT-COG	X	X	X	X	X	X	X
ISI	X	X	X	X	X	X	X
MFSI-SF	X	X	X	X	X	X	X
HADS	X	X	X	X	X	X	X
WPAI	X		X		X	X	X
Sleep Diaries*	Х	Х	Х	Х	Х	Х	Х
HLVT-R	X		Х		Х	Х	Х
COWAT	Х		Х		Х	Х	Х
Digit Span	X		Х		Х	Х	Х
BRIEF-A	Χ		Х		Х	Χ	Х
MMSE	Х						
Adverse				Х	Х		
Events							
Protocol							

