There are not currently plans to destroy the data. The data will be kept in a password protected and encrypted file and all identifiers will be stripped after completion of the trial.

11. TRIAL STEERING COMMITTEE:

We will convene a Trial Steering Committee (TSC) that consists of an independent chair and at least two other independent members, the nominated principal applicant, and the patient collaborator in the project. The TSC will meet quarterly throughout the study period to review: 1) the study protocol and any amendments and deviations: 2) rates of recruitment and retention; 3) any adverse events; 4) completeness of data collected; and 5) any other organizational problems or trial issues. The TSC will meet on an as needed basis to discuss adverse events, serving as the data safety monitoring board (DSMB). We deemed the TSC an appropriate DSMB given that adverse events associated with CBT-I are rare.

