14. AMENDMENTS

May 2023 – Increased sample size to 130 participants; added recruitment of qualitative exit interviews after trial completion.

May 2021 - Added study invitation mailout letters to patients from Atlantic Path study.

Memorial University of Newfoundland

May 30th, 2023

October 2020 – Eligibility criteria adjusted to allow individuals who have finished their cancer treatments 6 months prior to participate; added adverse event questionnaire at mid- and post-treatment.

September 2020 - Removal of participants wearing actigraphy watches (due to COVID-19).

June 2020 – Increased referrals from all Atlantic provinces instead of only Newfoundland and Labrador.

December 2019 – Added new recruitment strategy (local media and newspaper); added treatment fidelity (adherence, competence, etc.) as a component of the trial.

October 2019 – Added eligibility criteria for participants with hematological malignancies.

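### Adverse events are never asked about during the waitlist period, so self-reported events have no concurrent untreated comparison

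*Combined protocol and SAP*

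**What the plan says.** The adverse-event questions are described in Section 7.3: at the mid- and post-treatment assessments, "the participants will also be asked to complete questions related to adverse events during the CBT-I treatment". They are added to the Qualtrics assessment, and the free-text answers are to be grouped by theme into a record of events. No comparison between arms is planned for them.

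The two schedules in Section 7.6 follow that description. Table 1a, "Schedule of Assessments and Outcome Collection for Immediate Treatment", marks the adverse-event row at T1 (mid-treatment) and T2 (post-treatment). Table 1b, for the delayed arm, marks it at T3 (mid-treatment) and T4 (post-treatment). It is blank at T1 (monitoring) and T2 (pre-treatment). The October 2020 entry in Section 14 agrees: "added adverse event questionnaire at mid- and post-treatment".

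Section 4.1 describes the control period: "Participants in the waitlist control group will be required to monitor their sleep with sleep diaries for 8 weeks". CBT-I follows at once. Under Section 11 the Trial Steering Committee reviews adverse events and acts as the data safety monitoring board.

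**The concern.** The waitlist arm is untreated only from T0 to T2. Section 8.2.1 uses that window for the primary efficacy comparison, and Section 4.1 justifies the waitlist partly as a guard against regression to the mean. The same protection is not extended to adverse events, because every scheduled report comes from someone receiving CBT-I.

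This matters because the background complaints of this population can resemble effects of treatment. Section 3.1 describes fatigue, anxiety and depression linked to cancer treatment, and says that sleep loss impairs attention, executive function and memory. Section 6 includes sleep restriction among the treatment components. If a participant reports tiredness or poor concentration at mid-treatment, the adverse-event record offers no concurrent untreated frequency to set beside it. A raw count could then be read as harm when it is background, or dismissed as background when it is not.

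**Working it through.** **The schedules side by side, T0 to T2.** The row for each instrument is read from Tables 1a and 1b.

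| Instrument | Immediate arm | Delayed arm |
|---|---|---|
| Adverse-event questions | T1, T2 | none (first asked at T3) |
| FACT-Cog, ISI, MFSI-SF, HADS | T0, T1, T2 | T0, T1, T2 |

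The immediate arm has two scheduled adverse-event assessments in the randomised window and the delayed arm has none. The text of Section 7.3, both tables and the amendment entry all agree, so a misread table is not the explanation. The documents give no week number for T1, so I assume that monitoring in one arm and mid-treatment in the other fall at the same time.

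**Other routes to adverse events during the wait.** Section 9.1 has staff report distress that they notice, and Section 11 has the committee review any adverse events. Both can cover the waiting period, but neither is scheduled questioning, so neither yields a rate with a known denominator.

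**What the comparison would yield if it were collected.** The plan gives no figure for adverse events, so there is none to reproduce; its sample size concerns FACT-Cog only.

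- Participants: 130 at 1:1 (Sections 5.1 and 7.5), so 130/2 = 65 per arm.
- Event rate p: not in the documents. Assumed at 2%, 5%, 10%, 20% and 30%, equal in both arms.
- 95% half-width for the difference in proportions: h = 1.96 × √(2p(1−p)/65).

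| Assumed p | 2p(1−p)/65 | Square root | h |
|---|---|---|---|
| 2% | 0.000603 | 0.0246 | 4.8 points |
| 5% | 0.001462 | 0.0382 | 7.5 points |
| 10% | 0.002769 | 0.0526 | 10.3 points |
| 20% | 0.004923 | 0.0702 | 13.8 points |
| 30% | 0.006462 | 0.0804 | 15.8 points |

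At 2% the expected count is 65 × 0.02 = 1.3 events per arm. The normal approximation is poor there, and an exact method would be needed.

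**Detectable difference.** With two-sided alpha 0.05 and 80% power, a control rate of 10% needs a treated rate of about 29.4%. Check: the difference is 0.194 and the mean rate is 0.197, so (0.194 × √65 − 1.96 × √(2 × 0.197 × 0.803)) / √(0.10 × 0.90 + 0.294 × 0.706) = (1.564 − 1.102)/0.5455 = 0.85, which corresponds to power 0.80. For control rates of 20% and 30% the treated rates are about 42.6% and 54.0%. Only large differences could be detected.

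**As scheduled.** Waitlist adverse-event observations number 0 of about 65, so no difference can be estimated at any assumed rate.

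**The case against.** The strongest reply is that the trial does hold randomised information on harm. A reader might infer from the schedule that nothing about harm can be compared between arms. The documents do not support that. Worsening of anxiety or depression (HADS), fatigue (MFSI-SF), insomnia (ISI) and perceived cognition (FACT-Cog) can all be compared by randomised arm at T1 and T2. For fatigue and distress, the likeliest background complaints, concurrent untreated data will exist. What remains is that the plan does not designate these scales as safety outcomes, and that they would not record other events such as accidents.

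Two other strong readings also fail. One is that the trial throws safety data away; in fact the control-period answers are never collected. The other is that the questionnaire asks participants to blame CBT-I for what they report. The questionnaire is not in the documents, and the phrase in Section 7.3 says when the event occurred, not what caused it.

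It is also fair to say that the plan intends only a descriptive record, that it rates the risks as minimal and adverse events of CBT-I as rare, and that the primary endpoint is untouched. Precision would be coarse, and a difference that is not significant would not show safety. Participants also know their allocation, which can influence self-report. These points limit what the comparison could prove. They do not remove the value of a concurrent background rate.

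**Conclusion.** The gap is real and limited to self-reported adverse events. They are asked about twice in the immediate arm and never in the delayed arm during the only randomised treated-versus-untreated window, so they have no concurrent control.

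The figure of 65 per arm is an upper bound. Attrition would reduce it, and so would any participants who passed the window before the questions were added in October 2020; the documents do not say how many did. Given that bound, and assumed rates of 10%, 20% or 30%, the half-width is at best about 10, 14 or 16 points. The benefit is mainly a background frequency for reading on-treatment reports, with little power to test for harm. The efficacy analysis is not affected.

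**What to change.** 1. In Table 1b, add the adverse-event questions to the delayed arm's existing T1 and T2 Qualtrics assessments.
2. In Section 7.3, ask both arms about events since the last assessment, with T1 timed alike in the two arms so that recall periods match.
3. State an event definition and one coding scheme for the free-text answers, applied blind to arm where the content allows.
4. Report the T0 to T2 proportion with an event by randomised arm, and the difference with a 95% confidence interval, using an exact method if events are few.
5. Name worsening on HADS, MFSI-SF and ISI from T0 to T2 as safety summaries, reported by arm. This uses data already scheduled and works even where the wait is over.
6. For participants already past the wait, say in the report that their adverse-event data are uncontrolled.

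The cost is a few minutes of questionnaire time at two assessments that already exist and are already paid (Section 12.3), some coding of free text, and the extra tables. No visit or staff post is added.

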- Meet the DSM-5 criteria for insomnia disorder and have a score of 8 or greater on the Insomnia Severity Index^[2]

- Have good performance status as indicated by an ECOG score of 0-2.
- Have high-speed internet connection, webcam, and are fluent using the internet

5.3. Exclusion Criteria:

5.3.1 For individuals with and without hematological malignancies:

- Another sleep disorder, besides insomnia, that is not adequately treated (ie: untreated obstructive sleep, sleep apnea)
- The presence of another psychological disorder that is not currently stable and/or would impair the ability to participate in the study
- A major sensory deficit (e.g. blindness)
- A neurologic or major medical condition known to affect cognitive function (e.g., Parkinson's)
- A history of cranial radiation
- A history of any other condition that may affect cognitive functioning (e.g., traumatic brain injury)
- Previous experience with CBT-I

Participants will not be excluded for using psychotropic medication prior to study entry (e.g. antidepressants) provided that the dose was not recently altered (stable over the previous 6 weeks). Considering the potential for prescription of medications to help with sleep (e.g. hypnotics, sedatives, and antidepressants) within the cancer population, medication use throughout the study will be tracked and adjusted for in the statistical analysis.

5.4. Early Withdrawal of Participants:

Any participant withdrawing their consent to participate in the study or their authorization to use their protected health information will be withdrawn from the study. Participants withdrawn may be replaced, at the discretion of the principal investigator.

Reasons why participants are withdrawn will be documented on the Study Termination Form. Every effort will be made to continue to collect data on every participant for the entire study duration regardless of whether the participant continues to complete assessments, assuming the participant has not withdrawn his/her authorization to obtain such information.

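### The plan turns open-ended adverse-event answers into themes, plans no per-participant count of harms, and does not link withdrawal reasons or staff-noted distress to that record

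*Combined protocol and SAP*

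**What the plan says.** Section 7.3 sets the source: "At the mid and post treatment assessments, the participants will also be asked to complete questions related to adverse events during the CBT-I treatment". It then sets the method: "The open-ended Qualtrics responses will be thematically analyzed to create a record of adverse events experienced by the participants". Tables 1a and 1b in section 7.6 place the adverse-event form at T1 and T2 in the immediate group and at T3 and T4 in the delayed group, which are mid- and post-treatment in each case. The items on the form are not shown.

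Section 8 covers the primary and durability models, secondary and subsidiary analyses, missing data and sample size. It contains no analysis of harms.

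Other parts of the protocol also generate information about harm:

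- Section 5.4: "Reasons why participants are withdrawn will be documented on the Study Termination Form". The same section promises continued follow-up after a participant stops: "Every effort will be made to continue to collect data on every participant for the entire study duration". The exception is withdrawal of authorization.
- Section 8.2.2 records reasons for voluntary withdrawal for use in a sensitivity analysis, and provides for at least three calls after a missed visit.
- Section 9.1 has staff notify the principal investigator when a participant appears distressed, so that evaluation and treatment can follow.
- Section 6 provides for "weekly case supervision meetings including video review throughout the duration of the trial", with a session checklist that scores adherence to teaching points.

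Section 11 has the Trial Steering Committee (TSC) review adverse events quarterly and act as the data safety monitoring board (DSMB): "We deemed the TSC an appropriate DSMB given that adverse events associated with CBT-I are rare".

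**The concern.** Thematic analysis shows what kinds of problem participants describe. Unless a counting rule is added, it does not show how many participants had a problem, how severe it was, whether it was serious, or out of how many asked. The protocol adds no such rule in section 7.3 or section 8.

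The second difficulty is coverage. The form is scheduled at two points. A harm that leads someone to leave before the first of them may be written on the Study Termination Form, or noticed by staff, and still not enter the adverse-event record, because nothing in the text carries it there.

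What is at stake is the harm statement in the final report, and the information reaching a committee whose role as DSMB was justified by a premise about frequency. The primary comparison on the FACT-Cog does not depend on it.

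**Working it through.** The documents give no adverse-event rate, denominator or dropout rate, so there is no planned figure to reproduce. The check is mainly a comparison of sections.

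**Step 1: what output is planned.** Section 7.3 names one method, thematic analysis. Section 8 contains no harms summary. No section defines an adverse or serious event, or sets grading, attribution, a counting unit or a denominator. The planned output is therefore a set of themes.

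**Step 2: which sources feed the record.**

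| Source | Section | Stated use | Linked to the adverse-event record? |
|---|---|---|---|
| Mid- and post-treatment form | 7.3, Tables 1a and 1b | Thematic analysis | Yes |
| Withdrawal reasons | 5.4, 8.2.2 | Documentation; sensitivity analysis | Not stated |
| Distress noticed by staff | 9.1 | Notification for evaluation and treatment | Not stated |
| Session checklist, supervision, video review | 6 | Adherence and supervision | Not stated |

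Section 10.1 adds that recordings are deleted once reviewed. A harm voiced in a session and not written down then may not be recoverable.

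**Step 3: who can be missed.** The questions sit in the Qualtrics assessment, so answering them does not require attending therapy. Sections 5.4 and 8.2.2 keep trying to collect data from people who stop. The gap is certain only for those who withdraw authorization, or cannot be reached, before the mid-treatment form.

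**Step 4: direction and size.** Let d be the share of treated participants not captured by a form, p_c the event risk in those captured, and p_s the risk in those not captured. Assume that completers report their events.

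- True risk = (1 − d) × p_c + d × p_s
- Risk seen on the forms = p_c
- Difference = d × (p_s − p_c)

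The difference is zero if d = 0 (everyone is reached) or p_s = p_c (equal risk). It is an under-count if p_s > p_c. The documents give none of the three quantities, so no size can be stated.

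**Step 5: what a count would provide.** With zero events among N participants asked, the exact one-sided 95% upper bound on the risk is 1 − 0.05^(1/N).

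- N = 130 (planned recruitment): 1 − 0.05^(1/130) = 0.0228, or 2.3%.
- N = 65 (half of 130 under 1:1 allocation): 1 − 0.05^(1/65) = 0.0450, or 4.5%.

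These bounds assume that all N were asked and answered. A list of themes with no N gives no bound.

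**The case against.** The case on the other side has real weight.

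- **Continued collection.** A reader might infer that anyone harmed enough to stop CBT-I early drops out of the safety data. The documents do not support that. Section 5.4 commits to continued collection and section 8.2.2 to repeated calls, so a person who stops therapy may still complete the form. This stands, and it confines the certain loss to the group in step 3.
- **Other routes.** A reader might infer that the two forms are the sole source of safety information. Section 7.3 speaks of a record, not the only one, and section 11 has the TSC review any adverse events. This stands as a caution. What remains is that no section says how other information reaches either the record or the committee.
- **Themes can be counted.** Coded responses can be tallied per participant, and closed items on the unseen form cannot be ruled out. Both are true. The point is that the protocol commits to neither a tally nor an analysis of closed items.
- **The amendment log.** Section 14 dates the form to October 2020 ("added adverse event questionnaire at mid- and post-treatment"). A reader might infer that people treated earlier would be reported as event-free. The documents do not say how many there were, and no denominator is stated, so the plan makes no such error. Stating how many were never asked settles the question.
- **Importance.** Harm rates are not a study objective, and section 9.1 describes the risks as minimal. That limits the weight of the point. Section 11's reference to rarity is a general premise about CBT-I, not a claim that this trial undertook to prove.

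**Conclusion.** The point holds in limited form. The stated method commits to no per-participant count, severity, seriousness or denominator for harms, and the Study Termination Form and staff-noted distress are not linked to the adverse-event record. The record can therefore miss harms in participants who withdraw authorization or become unreachable before the mid-treatment form.

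The size of any under-count cannot be derived from the documents, and it may be zero under either condition in step 4. The conclusion rests on reading silence as absence of a planned rule, and on a form whose items are not shown. It does not touch the primary efficacy analysis. It is a worthwhile, low-cost improvement, not a flaw that threatens the trial's main result.

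**What to change.** Replace the analysis sentence in section 7.3, and add a short harms paragraph to section 8.2, to the following effect:

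1. Keep the open question. Code each response per participant: event, severity, serious or not, judged related or not.
2. Enter in the same log, marked by source, any harm given on the Study Termination Form, notified by staff as distress, or disclosed in a session and noted at the existing weekly supervision.
3. Report the number and percentage of participants with a solicited event, using as denominator those who were given and completed the form. Show the number completing it at each of the two time points.
4. Report events from other sources separately, with their source and the number of treated participants. Do not pool them with the solicited rate, because having attended a session does not mean having been asked.
5. State how many treated participants were never asked.
6. Keep the thematic analysis as a descriptive supplement.

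Cost: a coding sheet, brief notes at supervision, protocol wording, and time from someone qualified to judge severity and relatedness. No visits are added. Stored responses and termination forms can be coded retrospectively. Past session disclosures that were not written down probably cannot. The reported rate may look less favourable than a list of themes.
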